### **13.1.1.3 Documentation of Adverse Events**

All AEs will be collected from the time ICF is signed until the following time points:

- For subjects who do not enroll: until time of screen failure (e.g., screen failure, withdrawal of consent)
- For enrolled subjects who have a Safety Follow-up Visit: through the Safety Follow-up Visit
- For enrolled subjects in Parts A, B, and C who do not have a Safety Follow-up Visit, 10 days after the last dose of study drug
- For enrolled subjects in Part D who do not have a Safety Follow-up Visit, the earliest of
  - 28 days after the last dose of study drug, or
  - the ETT Visit, if that visit is 3 weeks or later following the last dose of study drug (see [Section 9.1.2.4](#))

All subjects will be queried, using nonleading questions, about the occurrence of AEs at each study visit. When possible, a constellation of signs and/or symptoms will be identified as 1 overall event or diagnosis. All AEs for enrolled subjects will be recorded in the CRF and source document. AEs for subjects who are screened but not subsequently enrolled in the study will be recorded only in the subject's source documents. The following data will be documented for each AE:

- Description of the event
- Classification of “serious” or “nonserious”
- Date of first occurrence and date of resolution (if applicable)
- Severity
- Causal relationship to study drug(s)
- Action taken
- Outcome
- Concomitant medication or other treatment given

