#### **9.1.1.3 Follow-up**

Subjects will have a Safety Follow-up Visit 7 to 10 days after the last study drug dose. Safety Follow-up Visit assessments are listed in [Table 3-2](#) (Cohorts A1 through A6 [up to A8]), [Table 3-3](#) (Cohort A3), [Table 3-4](#) (Cohort A9), [Table 3-5](#) (Part B), and [Table 3-6](#) (Part C).

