### **12.3.1 General Considerations**

Only descriptive analyses will be performed; no statistical hypothesis testing will be done. Continuous variables will be summarized using the following descriptive summary statistics: the number of subjects (n), mean, SD, SE, median, minimum value, and maximum value. Categorical variables will be summarized using counts and percentages.

All individual subject data for subjects who were randomized or received at least 1 dose of study drug will be presented in individual subject data listings.

For Parts A, B, and C, the **Treatment-emergent (TE) Period** will be from the first dose date of study drug to (1) the Safety Follow-up Visit for subjects who have a Safety Follow-up Visit, or (2) 7 days after the last dose of study drug for subjects who do not have a Safety Follow-up Visit.

For Part D, the **TE Period** will be from first dose date of study drug to 28 days after the last dose date of study drug.

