#### **12.3.4 Safety Analysis**

Safety is the primary objective of this study. The overall safety profile of VX-121 will be assessed in terms of the following primary (safety) endpoints:

- Incidence of treatment-emergent adverse events (TEAEs)
- Clinical laboratory values (including coagulation studies)
- ECG outcomes

- Vital signs
- Spirometry (Part D only)

Safety analyses will be based on the Safety Set. No statistical hypothesis testing will be conducted.

For safety variables, the baseline value will be defined as the most recent non-missing measurement collected before the initial administration of study drug.

All safety data will be presented in individual subject data listings.

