#### **12.3.4.1 Adverse Events**

AEs will be coded according to MedDRA. The number and percentage of subjects experiencing an AE will be summarized by the MedDRA System Organ Class (SOC) and Preferred Term (PT). AEs will be classified as pretreatment or treatment-emergent.

**Pretreatment AEs** are defined as AEs that were reported or worsened after signing the ICF up to the start of study drug dosing.

**TEAEs during the Treatment Period** are defined as any AE that worsened (either in severity or seriousness) or that was newly developed at or after the first dose date of study drug through the end of the TE Period for the Treatment Period.

Only TEAEs will be summarized in tables. All summaries of TEAEs will be presented by the severity of the AE and relationship to the study drug. Some rules that will apply to the summarization of AEs are (1) a subject with multiple occurrences of the same AE or a continuing AE will be counted only once; (2) only the maximum severity level will be presented in the severity summary; and (3) only the worst relationship level will be presented in the relationship summary.

AEs leading to death, other SAEs, dose interruption, and permanent discontinuation will be listed separately. All AEs through the Safety Follow-up Visit will be listed in an individual subject data listing, including pretreatment AEs.

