9 STATISTICAL ANALYSIS

9.1 General Considerations

The Schedule of Assessments is provided in Section 3 of CSP. The precision standards for reporting safety and efficacy variables are provided in an internal Biometrics document that specifies the programming rules including the precision for derived variables.

Continuous data will be summarized using the following descriptive summary statistics: the number of subjects (n), mean, standard deviation (SD), median, minimum value (min), and maximum value (max).

Categorical data will be summarized using frequency counts and percentages. Percentages will be presented to 1 decimal place, unless otherwise specified.

Treatment-emergent (TE) Period

For subjects participating in Part A (excluding Cohorts A3 and A9), Parts B and C, the **TE Period** will be from the first dose date of study drug to (1) the Safety Follow-up Visit for subjects who have a Safety Follow-up Visit, or (2) 7 days after the last dose of study drug for subjects who do not have a Safety Follow-up Visit.

For subjects participating in Cohort A3 in Part A, 2 TE periods will be analyzed:

- **TE Period 1 (suspension [fed])** will begin from the administration of study drug on Day 1 (1) until the administration of VX-121 in fed state and with milk, or (2) the Safety Follow-up Visit for subjects who do not have the dose of VX-121 in fed state and with milk, and have a Safety Follow-up Visit, or (3) 7 days after the last dose of study drug for subjects who do not have the dose of VX-121 in fed state and with milk, and do not have a Safety Follow-up Visit.
- **TE Period 2 (suspension [fed and with milk])** will begin from the administration of study drug on Day 9 through the Safety Follow-up Visit or 7 days after the last dose of study drug, whichever comes first.

For subjects participating in Cohort A9 in Part A, 3 TE periods will be analyzed:

- **TE Period 1 (suspension [fed])** will begin from the administration of study drug on Day 1 (1) until the administration of VX-121 tablet in the fed state, or (2) the Safety Follow-up Visit for subjects who do not have the dose of VX-121 tablet in the fed state and have a Safety Follow-up Visit, or (3) 7 days after the last dose of study drug for subjects who do not have the dose of VX-121 tablet in the fed state and do not have a Safety Follow-up Visit.

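### SAP 9.1 closes Cohort A3 TE Period 2 at day 7 after the last dose even when the Safety Follow-up Visit falls on days 8 to 10; a minor 7-day versus 10-day mismatch also affects Parts A to C subjects without that visit

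*Protocol*

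**What the plan says.** **Visit timing.** Protocol 9.1.1.3, for Parts A to C: "Subjects will have a Safety Follow-up Visit 7 to 10 days after the last study drug dose".

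**TE Period in the protocol.** Section 12.3.1 gives one rule for Parts A, B and C. The period runs from first dose to the Safety Follow-up Visit where there is one, and otherwise to "7 days after the last dose of study drug for subjects who do not have a Safety Follow-up Visit".

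**TE Period in the SAP.** Section 9.1 keeps that rule for Parts B and C and for Part A apart from Cohorts A3 and A9. It splits A3 into two periods and A9 into three. A3 TE Period 2 starts with the Day 9 open-label dose given with milk and runs "through the Safety Follow-up Visit or 7 days after the last dose of study drug, whichever comes first". A9 TE Period 3 is also the last period of its cohort. It runs to the visit, and its 7-day limit applies only to subjects who have no visit.

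**AE collection.** Protocol 13.1.1.3 has one rule for attenders: "For enrolled subjects who have a Safety Follow-up Visit: through the Safety Follow-up Visit". For enrolled Parts A to C subjects "who do not have a Safety Follow-up Visit, 10 days after the last dose of study drug" is the end point.

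**What reaches the tables.** Protocol 12.3.4.1: "Only TEAEs will be summarized in tables". SAP 9.4.1 has the same restriction and, for A3 and A9, assigns TEAEs by start date within the corresponding TE period.

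**The concern.** The TE Period decides which collected AEs are tabulated. In Cohort A3 the final TE period can end before the follow-up visit that closes AE collection, although the protocol defines the TE Period for these subjects as running to that visit. The visit generates safety data: Table 3-3 schedules ECG, vital signs, physical examination, chemistry, hematology and urinalysis there, and clinically significant findings are reported as AEs. A new finding dated to a visit on day 8, 9 or 10 would be neither pretreatment nor treatment-emergent. Protocol 12.3.4.1 and SAP 9.4.1 offer no third class. A post-treatment class appears only in SAP Appendix C, which SAP 9.4.1 confines to Part D.

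The same kind of gap arises on a smaller scale for Parts A to C subjects with no visit, whose AE collection runs 3 days beyond their TE Period. At stake is whether the TEAE tables contain the post-dose events that the trial collected.

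**Working it through.** The plan states no figure to reproduce. The check sets the windows side by side.

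**Inputs.** Last planned dose by cohort (Tables 3-2 to 3-6): Day 1 in the single-dose cohorts, Day 9 in A3, Day 17 in A9, Day 10 in Part B, Day 14 in Part C. Visit: last dose + 7 to + 10 (Protocol 9.1.1.3). TE end without a visit: last dose + 7 (Protocol 12.3.1, SAP 9.1). Collection end without a visit: last dose + 10 (Protocol 13.1.1.3).

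| Cohort | Last dose | Visit due | TE end, visit held (SAP) | TE end, no visit | Collection end, no visit |
|---|---|---|---|---|---|
| Single-dose Part A | Day 1 | Days 8–11 | visit | Day 8 | Day 11 |
| A3 (Period 2) | Day 9 | Days 16–19 | **Day 16** | Day 16 | Day 19 |
| A9 (Period 3) | Day 17 | Days 24–27 | visit | Day 24 | Day 27 |
| Part B | Day 10 | Days 17–20 | visit | Day 17 | Day 20 |
| Part C | Day 14 | Days 21–24 | visit | Day 21 | Day 24 |

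**Cohort A3, visit held.** Write v for the visit day counted from the last dose, with v between 7 and 10.

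- SAP window: min(v, 7) = 7, whatever v is.
- Protocol window: v.
- Collection: v.
- Days collected but outside the SAP window: v − 7, that is 0, 1, 2 or 3.

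With about 8 subjects the most that can be lost is 8 × 3 = 24 subject-days, all after active drug, because every A3 subject receives VX-121 on Day 9. A3 is the only row in which an attender's TE Period can end before an on-schedule visit.

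**Parts A to C, no visit.** Gap = 10 − 7 = 3 days per subject. The documents give no rate of missed visits. Planned subjects in Parts A to C: 56 + 48 + 16 = 120. Assuming that 0% to 10% miss the visit, 0 to 12 subjects are exposed. Only events that start or worsen inside those 3 days are affected; events that began earlier and continue are already counted.

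**Part D, for comparison.** SAP 9.1 runs the TE Period to the visit, or to 28 days after the last dose without one. Protocol 13.1.1.3 also uses 28 days without a visit, except where a late early-termination visit ends collection sooner. The 7-versus-10 gap is specific to Parts A to C.

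**The case against.** **The events are not lost.** This stands. AEs of enrolled subjects are recorded in the CRF, individual data are listed, and SAEs and AEs leading to death, interruption or discontinuation are listed separately. Cohorts of about 8 can be read subject by subject. One qualification: the AE listing is described as running through the Safety Follow-up Visit, which sets no end point for a subject without one.

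**Few such events would exist without a visit.** This also stands. AEs are queried at study visits. Discharge comes 4 days after the last dose in most of Part A and in Parts B and C, and 7 days after it in A3 and A9; the only later scheduled contact is the visit itself. Events on days 8 to 10 would come from spontaneous reports or from efforts to reach the subject, and nothing is collected after consent is withdrawn. AEs whose missing or partial start date leaves the timing unclear default to treatment-emergent (SAP 9.4.1).

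**Seven days is a coherent no-visit limit.** Partly true. It equals the shortest window an attender can have, and nothing requires the TE and collection windows to be equal. But no reason is given for collecting to day 10 and tabulating to day 7.

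**A fixed A3 window might be meant to resemble Period 1,** which lasts 9 − 1 = 8 days. The SAP does not say so. The same argument would apply to A9, whose first two periods are also 8 days apart, yet A9 TE Period 3 runs to the visit.

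**Stronger readings.** A reader might infer that the sole primary endpoint is compromised. TEAE incidence is one of several safety measures in Protocol 12.3.4, all descriptive and without hypothesis testing. A reader might infer that subjects who do not return are those for whom late AEs matter most; nothing in the documents supports that. A reader might take 3/10 = 30% as the general size. That fraction counts only days after the last dose. Over the study days from first dose to collection end it is 3/11 = 27% in single-dose cohorts, 3/19 = 16% in A3, 3/27 = 11% in A9, 3/20 = 15% in Part B and 3/24 = 12.5% in Part C, and it says nothing about how many subjects are affected.

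**Conclusion.** The A3 clause is a real conflict between the SAP and Protocol 12.3.1, and a departure from the SAP's own treatment of A9 TE Period 3. It does not depend on missed visits. Applied as written, it ends the window at day 7 for about 8 subjects on open-label VX-121 and keeps up to 3 days of collected AEs per subject out of the TEAE tables. This assumes that the subject received the milk dose and that the visit was on schedule; a visit on day 7 loses nothing.

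The no-visit mismatch is real but minor: 3 days per subject, in a number of subjects that the documents do not give and that is probably very small. The range of 0 to 12 rests wholly on the assumed 0% to 10% rate of missed visits.

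Neither item affects a test or an error rate. What is affected is the completeness of the descriptive TEAE tables.

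**What to change.** In SAP 9.1:

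1. Replace "7 days after the last dose of study drug, whichever comes first" in Cohort A3 TE Period 2 with the construction used for A9 TE Period 3: through the Safety Follow-up Visit, or a fixed number of days after the last dose for subjects who have no visit.
2. Set that fixed number to 10 days in every Parts A to C no-visit clause (the general clause, both A3 periods and all three A9 periods), to match AE collection in Protocol 13.1.1.3.

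The SAP provides for amendment before database lock, and it already refines the protocol's TE Period for Part D, so a SAP amendment is enough. Protocol 12.3.1 can be aligned at its next amendment; a protocol change on its own would need investigator and sponsor approval and regulatory submission (Protocol 13.2.3).

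No new data are needed, and TEAE counts can only stay the same or rise slightly. The change does not equalise follow-up: attenders' windows would still vary from 7 to 10 days with the visit date, and a subject with no visit would have a longer nominal window than one seen on day 7. Its purpose is to make the tabulated period match the collected period.

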### **13.1.1.4 Adverse Event Severity**

#### **13.1.1.4.1 Parts A, B, and C**

The investigator will determine and record the severity of all serious and nonserious AEs. The guidance available at the following website will be consulted: Toxicity Grading Scale for Healthy Adult and Adolescent Volunteers Enrolled in Preventive Vaccine Clinical Trials, September 2007, Center for Biologics Evaluation and Research, <http://www.fda.gov/BiologicsBloodVaccines/GuidanceComplianceRegulatoryInformation/Guidances/Vaccines/ucm074775.htm> (Accessed November 2017). The severity of an AE that does not appear in this scale will be determined according to the definitions in [Table 13-1](#).

**Table 13-1 Grading of AE Severity**

Classification	Definition
Mild (Grade 1)	Mild level of discomfort and does not interfere with regular activities
Moderate (Grade 2)	Moderate level of discomfort and significantly interferes with regular activities
Severe (Grade 3)	Significant level of discomfort and prevents regular activities
Life-threatening (Grade 4)	Any adverse drug event that places the subject, in the view of the investigator, at immediate risk of death

**13.1.1.4.2 Part D**

The investigator will determine and record the severity of all serious and nonserious AEs. The guidance available at the following website will be consulted: Common Terminology Criteria for Adverse Events (CTCAE), Version 4.0, Cancer Therapy Evaluation Program, [http://ctep.cancer.gov/protocolDevelopment/electronic\\_applications/ctc.htm](http://ctep.cancer.gov/protocolDevelopment/electronic_applications/ctc.htm) (Accessed November 2017). AEs of CTCAE Grades 4 and 5 will be documented as “life-threatening.” The severity of an AE that does not appear in the CTCAE will be determined according to the definitions in Table 13-2.

**Table 13-2 Grading of AE Severity**

Classification	Definition
Mild (Grade 1)	Mild level of discomfort and does not interfere with regular activities
Moderate (Grade 2)	Moderate level of discomfort and significantly interferes with regular activities
Severe (Grade 3)	Significant level of discomfort and prevents regular activities
Life-threatening (Grade 4)	Any adverse drug event that places the subject, in the view of the investigator, at immediate risk of death

**13.1.1.5 Adverse Event Causality**

Every effort will be made by the investigator to assess the relationship of the AE, if any, to the study drug(s). Causality will be classified using the categories presented in Table 13-3.

**Table 13-3 Classifications for AE Causality**

Classification	Definition
Related	There is an association between the event and the administration of investigational study drug, a plausible mechanism for the event to be related to the investigational study drug and causes other than the investigational study drug have been ruled out, and/or the event reappeared on re-exposure to the investigational study drug.
Possibly related	There is an association between the event and the administration of the investigational study drug and there is a plausible mechanism for the event to be related to investigational study drug, but there may also be alternative etiology, such as characteristics of the subject's clinical status or underlying disease.
Unlikely related	The event is unlikely to be related to the investigational study drug and likely to be related to factors other than investigational study drug.
Not related	The event is related to an etiology other than the investigational study drug (the alternative etiology will be documented in the study subject's medical record).

**Table 13-3 Classifications for AE Causality**

Classification	Definition
----------------	------------

**13.1.1.6 Study Drug Action Taken**

The investigator will classify the study drug action taken with regard to the AE. The action taken will be classified according to the categories shown in Table 13-4.

**Table 13-4 Classifications for Study Drug Action Taken With Regard to an AE**

Classification	Definition
Dose not changed	Study drug dose not changed in response to an AE
Dose reduced	Study drug dose reduced in response to an AE
Drug interrupted	Study drug administration interrupted in response to an AE
Drug withdrawn	Study drug administration permanently discontinued in response to an AE
Not applicable	Action taken regarding study drug administration does not apply. “Not applicable” will be used in circumstances such as when the investigational treatment had been completed before the AE began and no opportunity to decide whether to continue, interrupt, or withdraw treatment is possible.

**13.1.1.7 Adverse Event Outcome**

An AE will be followed until the investigator has determined and provided the final outcome. The outcome will be classified according to the categories shown in Table 13-5.

**Table 13-5 Classifications for Outcome of an AE**

Classification	Definition
Recovered/resolved	Resolution of an AE with no residual signs or symptoms
Recovered/resolved with sequelae	Resolution of an AE with residual signs or symptoms
Not recovered/not resolved (continuing)	Either incomplete improvement or no improvement of an AE, such that it remains ongoing
Fatal	Outcome of an AE is death. “Fatal” will be used when death is at least possibly related to the AE.
Unknown	Outcome of an AE is not known (e.g., a subject lost to follow-up)

**13.1.1.8 Treatment Given**

The investigator ensures adequate medical care is provided to subjects for any AEs, including clinically significant laboratory values related to study drug. In addition, the investigator will describe whether any treatment was given for the AE. “Yes” is used if any treatment was given in response to an AE, and may include treatments such as other medications, surgery, or physical therapy. “No” indicates the absence of any kind of treatment for an AE.

## **13.1.2        Serious Adverse Events**

### **13.1.2.1      Definition of a Serious Adverse Event**

An SAE is any AE that meets any of the following outcomes:

- Fatal (death, regardless of cause, that occurs during participation in the study or occurs after participation in the study and is suspected of being a delayed toxicity due to administration of the study drug)
- Life-threatening, such that the subject was at immediate risk of death from the reaction as it occurred
- Inpatient hospitalization or prolongation of hospitalization
- Persistent or significant disability/incapacity (disability is defined as a substantial disruption of a person's ability to conduct normal life functions)
- Congenital anomaly or birth defect
- Important medical event that, based upon appropriate medical judgment, may jeopardize the subject or may require medical or surgical intervention to prevent 1 of the outcomes listed above (e.g., an allergic bronchospasm requiring intensive treatment in an emergency room or at home)

If a subject has a hospitalization or procedure (e.g., surgery) for an event or condition that occurred before the subject signed the ICF, and the hospitalization or procedure was planned before the subject signed the ICF, the hospitalization or procedure will not be considered to indicate an SAE, unless an AE caused the hospitalization or procedure to be rescheduled sooner or to be prolonged relative to what was planned. In addition, hospitalizations clearly not associated with an AE (e.g., social hospitalization for purposes of respite care) will not be considered to indicate an SAE.

Clarification will be made between the terms “serious” and “severe” because they are not synonymous. The term “severe” is often used to describe the intensity (severity) of a specific event, as in mild, moderate, or severe myocardial infarction. The event itself, however, may be of relatively minor medical significance, such as a severe headache. This is not the same as “serious,” which is based on subject/event outcome or action described above, and is usually associated with events that pose a threat to a subject’s life or functioning. Seriousness, not severity, serves as a guide for defining expedited regulatory reporting obligations.

